## 5.2 Exclusion criteria

Patients must not meet any of the following exclusion criteria at screening:

1. Patients with compression of the optic chiasm causing any visual field defect that requires surgical intervention
2. Diabetic patients with poor glycemic control as evidenced by HbA1c >8%
3. Patients with risk factors for torsade de pointes, i.e. patients with a baseline QTcF >450 ms in males, and > 460 ms in females. hypokalemia, hypomagnesaemia, uncontrolled hypothyroidism, family history of long QT syndrome, or concomitant medications known to prolong QT interval
4. Patients with clinically significant valvular disease
5. Patients with Cushing's syndrome due to ectopic ACTH secretion
6. Patients with hypercortisolism secondary to adrenal tumors or nodular (primary) bilateral adrenal hyperplasia
7. Patients who have a known inherited syndrome as the cause for hormone over-secretion (i.e. Carney Complex, McCune-Albright syndrome, MEN-1)
8. Patients who are hypothyroid and not on adequate replacement therapy
9. Patients with symptomatic cholelithiasis
10. Patients who have congestive heart failure (NYHA Class III or IV), unstable angina, sustained ventricular tachycardia, clinically significant bradycardia, advanced heart block, history of acute MI less than one year prior to study entry or clinically significant impairment in cardiovascular function
11. Patients with liver disease such as cirrhosis, chronic active hepatitis, or chronic persistent hepatitis, or patients with ALT/AST > 2 X ULN, serum bilirubin >2.0 X ULN
12. Patients with serum creatinine >2.0 X ULN
13. Patients with WBC <3 X 10^9/L; Hb 90% < LLN; PLT <100 X 10^9/L
14. Patients who have a history of alcohol or drug abuse in the 6 month period prior to receiving pasireotide
15. Patients who have participated in any clinical investigation with an investigational drug within 1 month prior to dosing
16. Patients with active malignant disease within the last five years (with the exception of basal cell carcinoma or carcinoma in situ of the cervix)
17. Patients with the presence of active or suspected acute or chronic uncontrolled infection
18. Patients with a history of non-compliance to medical regimens or who are considered potentially unreliable or will be unable to complete the entire study
19. Patients with presence of Hepatitis B surface antigen (HbsAg)
20. Patients with presence of Hepatitis C antibody test (anti-HCV)
21. Patients with severe hepatic impairment (Child Pugh C) and hypersensitivity to pasireotide or cabergoline
22. Patients with lung, pericardial, and retroperitoneal fibrosis; gastro-duodenal ulcer or digestive hemorrhage, galactose intolerance, Parkinson's disease, uncontrolled hypertension and Raynaud's syndrome.

23. Pregnant or nursing (lactating) women where pregnancy is defined as the state of a female after conception and until the termination of gestation, confirmed by a positive hCG laboratory test ( $> 5$  mIU/mL).
24. Patients with end-stage renal failure and/or hemodialysis

## **6 Treatment**

### **6.1 Patient numbering, treatment assignment**

Each patient is identified in the study by a Subject Number (Subject No.), that is assigned when the patient is first enrolled for screening and is retained as the primary identifier for the patient throughout his/her entire participation in the trial. The Subject Number is a 9-digit number consists of the Center Number (Center No.) (as assigned by Novartis to the investigative site) with a sequential patient number suffixed to it, so that each subject is numbered uniquely across the entire database. Upon signing the informed consent form, the patient is assigned to the next sequential Subject No. available to the investigator. Once assigned, the Subject No. must not be reused for any other subject and the Subject No. for that individual must not be changed, even if the patient is re-screened. If the patient fails to be assigned to treatment for any reason, the reason will be entered into the Screening Disposition page

### **6.2 Study treatment**

Patients who are not treated with pasireotide at the time of screening or have never been treated with pasireotide in the past will start pasireotide 0.6mg twice a day for 8 weeks. If biochemical control is not achieved by the end of 8 weeks, and the 0.6mg dose is well-tolerated, the dose of pasireotide will be increased to 0.9mg twice a day for another 8 weeks. If biochemical control is not achieved with the higher dose of pasireotide, cabergoline will be added and patients will begin combination treatment with cabergoline at the starting dose of 0.5mg qd for 8 weeks. If biochemical control is still not achieved at the end of the third 8-week treatment period, the dose of cabergoline will be further increased to cabergoline at 1.0mg qd for another 8 weeks.

Patients that cannot have the dose up-titrated to 0.9mg bid because of safety reasons, for example, significantly increased blood glucose levels, will be treated with combination pasireotide 0.6mg bid and cabergoline at increasing doses. Patients who cannot tolerate pasireotide 0.6mg bid will have the dose down-titrated to 0.3mg bid and begin combination treatment with cabergoline at increasing doses should pasireotide 0.3mg bid monotherapy not be able to lead to normal mUFC. If a patient shows high sensitivity to pasireotide 0.6 mg bid resulting in cortisol values  $<LLN$  and/or signs/symptoms consistent with the diagnosis of hypocortisolism, the dose of pasireotide can be decreased to 0.3 mg bid. Despite the dose reduction, some patients may still present with cortisol values  $<LLN$  and/or signs/symptoms consistent with hypocortisolism; in this case the dose of pasireotide can be further reduced to 0.3 mg qd in order to achieve and maintain normal cortisol levels. Please refer to Dose modifications and titration guidelines [Section 6.4](#) of the protocol for more details.

At weeks 8, 17 and 26, patients will continue to receive their current dose until their UFC results are available, at which time, a decision will be made on whether to maintain the current dose or titrate up to the next level.

Patients who are currently treated with maximal tolerated doses of pasireotide monotherapy at 0.3mg, 0.6mg or 0.9mg twice a day for at least 8 weeks, but still with elevated UFC will immediately start the combination treatment by adding cabergoline 0.5mg once a day to their current pasireotide dose at study entry. Patients will continue with the combination treatment for 8 weeks. If biochemical control is not achieved by the end of the 8 weeks, the dose of cabergoline will be increased to 1mg once a day. At week 8, patients will continue to receive their starting combination dose until their UFC results are available, at which time, a decision will be made on whether to maintain the current dose or titrate up to the next combination dose.

All patients will be treated for a total of 35 weeks in the core phase.

The possible monotherapy or combination treatment regimens are as follows:

1. Monotherapy: pasireotide 0.3mg twice a day
2. Monotherapy: pasireotide 0.6mg twice a day
3. Monotherapy: pasireotide 0.9mg twice a day
4. Combination: pasireotide 0.3mg twice a day + cabergoline 0.5mg once a day
5. Combination: pasireotide 0.3mg twice a day + cabergoline 1.0mg once a day
6. Combination: pasireotide 0.6mg twice a day + cabergoline 0.5mg once a day
7. Combination: pasireotide 0.6mg twice a day + cabergoline 1.0mg once a day
8. Combination: pasireotide 0.9mg twice a day + cabergoline 0.5mg once a day
9. Combination: pasireotide 0.9mg twice a day + cabergoline 1.0mg once a day
10. Monotherapy: pasireotide 0.3mg once a day\*

\* This dosage should only be applied if a patient shows high sensitivity to pasireotide 0.6 mg bid resulting in cortisol values <LLN and/or signs/symptoms consistent with the diagnosis of hypocortisolism, the dose of pasireotide can be decreased to 0.3 mg bid. Despite the dose reduction, some patients may still present with cortisol values <LLN and/or signs/symptoms consistent with hypocortisolism; in this case the dose of pasireotide can be further reduced to 0.3 mg qd in order to achieve and maintain normal cortisol levels.

### **6.2.1 Dosing regimen**

For dose and treatment schedule, please see Table 6-1 below.

**Table 6-1 Dose and treatment schedule**

Study treatments	Pharmaceutical form and route of administration	Dose	Frequency and/or Regimen
Pasireotide	Subcutaneous	0.3mg, 0.6mg, and 0.9mg	Twice a day
Cabergoline	Oral	0.5mg or 1.0mg	Once a day

## **6.2.2 Treatment duration**

### **Core phase**

All patients will receive a total of 35-week treatment.

### **Extension phase**

After up to 35 weeks of treatment, patients have the option to continue study treatment if pasireotide is not approved for commercial use and/or reimbursed in each respective country, if country reimbursement is applicable. Patients can continue with study treatment on extension phase until pasireotide is approved for commercial use and reimbursed in their respective country, or until 31st December, 2019, or once an applicable roll over protocol becomes available, or whichever occurs first.

## **6.3 Study drug**

### **6.3.1 Supply, preparation and storage**

### **6.3.2 Pasireotide**

Please refer to pasireotide Package Insert and Summary of Product Characteristics (SmPC) for preparation and storage. Pasireotide will be supplied by Novartis if it is not available in the respective country.

### **6.3.3 Cabergoline**

Cabergoline is in the form of 0.5mg tablet. Cabergoline should be taken in the evening after a full meal. Dostinex, a generic form of cabergoline, will be used in the trial. If Dostinex is not available in a participating country, a different type of generic form will be used. For storage conditions, please refer to cabergoline Package Insert and SmPC. Cabergoline will be supplied by Novartis.

### **6.3.4 Study drug compliance**

Patients must be able to self-administer the study drug, pasireotide (subcutaneous injections) and are to receive instruction from the site staff or investigator on the correct procedures. They should be advised to avoid multiple injections at, or near the same site. Ampoules will not be reused; a new ampoule should be used for each injection. Patients should be instructed to retain and return unused ampoules at their next scheduled visit.

Patients will self-administer pasireotide subcutaneously twice a day 12 hours apart. It is advised to take the study medication at the same time every day at around 10:00 in the morning and 10:00 in the evening.

For patients who are unable to tolerate the protocol specified dosing schedule, dose adjustments are permitted to keep the patient on study drug. Please refer to the Dose Modification and Titration Guidelines section.

The investigator should instruct the patient to take the study drug exactly as described. All dosages prescribed and dispensed to the patient and all dose changes during the study must be recorded on the Dosage Administration Record Case Report Form (CRF).

Patient should phone the investigator if he/she experiences an adverse event and their next study visit is not yet due. If dose delay or modification is required due to the adverse event, the investigator should document in the medical record the telephone conversation regarding the dose delay or modification.

## **6.4 Guidelines for dose modifications and titrations**

### **6.4.1 Pasireotide and cabergoline dose modification steps**

**Pasireotide untreated patients:** will begin their treatment with pasireotide 0.6mg twice a day monotherapy for 8 weeks. If biochemical control is not achieved by the end of the 8-week period, and the 0.6mg dose is well tolerated, the dose of pasireotide will be increased to 0.9mg twice a day for another 8 weeks. If biochemical control is still not achieved at 0.9mg twice a day and the dose is well tolerated, the combination treatment of pasireotide 0.9mg twice a day plus cabergoline 0.5mg once a day will be given for another 8 weeks. If biochemical control is not yet achieved either during or at the end of the 8-week period, cabergoline dose will be increased to 1.0mg once a day.

If a patient shows high sensitivity to pasireotide 0.6mg bid resulting in cortisol values <LLN and/or signs/symptoms consistent with the diagnosis of hypocortisolism, the dose of pasireotide can be decreased to 0.3mg bid. Despite the dose reduction, some patients may still present with cortisol values <LLN and/or signs/symptoms consistent with hypocortisolism; in this case the dose of pasireotide can be further reduced to 0.3 mg qd in order to achieve and maintain normal cortisol levels.

If the 0.9mg twice a day dose is not tolerated and biochemical control is not achieved, patient will begin combination treatment of pasireotide at 0.6mg twice a day plus cabergoline at 0.5mg once a day for 8 weeks. If during or at the end of the 8-week period, the biochemical control is not achieved, the combination dose will be increased to pasireotide at 0.6mg twice a day plus cabergoline at 1.0mg once a day for 8 weeks. The patient will continue with the highest combination dose of 0.6mg pasireotide twice a day plus 1.0mg cabergoline once a day, or 0.9mg pasireotide twice a day plus 1.0mg of cabergoline once a day for 8 weeks. The total duration of treatment is 35 weeks. (see [Table 6-2](#))

If patient does not tolerate 0.6mg twice a day, the dose of pasireotide should be decreased to 0.3mg twice a day. If pasireotide 0.3mg twice a day does not lead to biochemical control after at least 8 weeks of treatment, combination with cabergoline as described above can be initiated (see [Table 6-2](#)).

If patient cannot increase from 0.6mg twice a day to 0.9mg twice a day due to safety, and is not yet biochemically controlled, combination with cabergoline 0.5mg qd can be initiated right away with pasireotide at 0.6mg twice a day (see [Table 6-2](#)).

If patient is being escalated to 0.9mg twice a day, but cannot tolerate the dose, dose should be reduced to 0.6mg twice a day. If the latter dose does not lead to biochemical control, combination with cabergoline as described above can be initiated (see [Table 6-2](#)).

If combination pasireotide and cabergoline 0.5mg once a day is not tolerated, the dose of cabergoline can be reduced to 0.5mg every other day. If 0.5mg every other day is not tolerated, and biochemical control is not achieved, patient should be considered for discontinuation if no clinical benefit is derived (see [Table 6-2](#)).

If combination pasireotide and cabergoline 1.0mg once a day is not tolerated, the dose of cabergoline can be reduced to 1.0mg every other day. If 1.0mg every other day is not tolerated, and biochemical control is not achieved, patient should be considered for discontinuation if no clinical benefit is derived (see [Table 6-2](#)).

The minimum treatment of any regimen is 8 weeks. Patients losing biochemical control at any time point after the 8 week period will have the dose of the study medication increased immediately to the next level provided that the dose is well tolerated.

For patients whose starting dose is 0.6mg pasireotide twice a day monotherapy, at weeks 9, 18 and 27, before patient's UFC results are available, the investigator may select one of the following two options to dispense study medication to the patient for the next 5-9 weeks of treatment:

Option 1: The investigator dispenses study medication at the current dose, plus study medication at the next dose level at the end of week 8, 13, 17, 22, 26, or 31 visits. When patient's UFC results are available, the investigator should phone the patient to inform him/her to either remain at the current dose or titrate up to the next monotherapy dose level or start the combination therapy.

Option 2: The investigator dispenses study medication at the current dose at the end of week 8, 13, 17, 22, 26 or 31 visits. When patient's UFC results are available and shown that his/her biochemical is not controlled, the investigator schedules a visit for patient to come to the clinic and pick up study medication at the next monotherapy dose level or start the combination therapy.

The dosing decision should be properly documented in the medical record and dose administration CRF page.

**Table 6-2 Pasireotide and cabergoline dose modification steps for pasireotide un-treated patients**

Pasireotide: pasi Cabergoline: cabe	Starting dose level	Dose modification level - 1	Dose modification level - 2	Dose modification level - 3	Dose medication level - 4
Modification # 1	0.6mg bid pasi a	0.3mg bid pasi b	0.3mg bid pasi + 0.5mg cabe qd b	0.3mg bid pasi + 1.0mg cabe qd	
Modification # 2	0.6mg bid pasi b	0.9mg bid pasi b	0.9mg bid pasi + 0.5mg qd cabe b	0.9mg bid pasi + 1.0mg qd cabe	
Modification # 3	0.6mg bid pasi b	0.9mg bid pasi a	0.6mg bid pasi b	0.6mg bid pasi + 0.5mg cabe qd b	0.6mg bid pasi + 1.0mg cabe qd
Modification # 4	0.6mg bid pasi c	0.6mg bid pasi + 0.5mg qd cabe b	0.6mg bid pasi + 1.0mg cabe qd		
Modification # 5	0.9mg bid pasi ab	0.6mg bid pasi + 0.5mg qd cabe b	0.6mg bid pasi + 1.0mg qd cabe		

Pasireotide: pasi Cabergoline: cabe	Starting dose level	Dose modification level - 1	Dose modification level - 2	Dose modification level - 3	Dose modification level - 4
Modification # 6	0.3, 0.6 or 0.9mg bid pasi + 0.5mg qd cabe a	0.3, 0.6 or 0.9mg bid pasi + 0.5mg every other day cabe ab	Discontinuation if no clinical benefit		
Modification # 7	0.3, 0.6 or 0.9mg bid pasi + 1.0mg qd cabe a	0.3, 0.6 or 0.9 mg bid pasi + 1.0mg every other day cabe ab	Discontinuation if no clinical benefit		

a Dose modification is initiated if the current dose is not tolerated

b Dose modification is initiated if biochemical control is not achieved

c Dose cannot be increased to the next level due to toxicity but biochemical control is not achieved

**Patients currently treated with maximal tolerated doses of pasireotide monotherapy:**

0.3mg bid, 0.6mg bid or 0.9mg bid, for at least 8 weeks but did not achieve biochemical control will begin their combination treatment of pasireotide at 0.3mg, 0.6mg or 0.9mg bid plus 0.5mg of cabergoline once a day at study entry. They will continue the treatment for 8 weeks. If biochemical control is not achieved at the end of the 8-week period, the dose of cabergoline will be increased to 1.0mg once a day and continue with the combination treatment for the remainder of 26 weeks.

If combination pasireotide and cabergoline 0.5mg once a day is not tolerated, the dose of cabergoline can be reduced to 0.5mg every other day. If 0.5mg every other day is not tolerated, and biochemical control is not achieved, patient should be considered for discontinuation if no clinical benefit is derived (see [Table 6-3](#)).

If combination pasireotide and cabergoline 1.0mg once a day is not tolerated, the dose of cabergoline can be reduced to 1.0mg every other day. If 1.0mg every other day is not tolerated, and biochemical control is not achieved, patient should be considered for discontinuation if no clinical benefit is derived (see [Table 6-3](#)).

The minimum treatment of any regimen is 8 weeks. Patients losing biochemical control at any time point after the 8-week treatment period at the starting combination dose will have the dose of the study medication increased immediately to the next level provided that the dose is well tolerated (see [Table 6-3](#)).

At week 9, before patient's UFC results are available, the investigator may select one of the following two options to dispense study medication to the patient for the next 26 weeks of treatment:

Option 1: The investigator dispenses study medication at the current dose, plus study medication at the next dose level at the end of week 8 visit. When patient's UFC results are available, the investigator should phone the patient to inform him/her to either remain at the current dose or titrate up to the next combination dose level.

Option 2: The investigator dispenses study medication at the current dose at the end of week 8 visit. When patient's UFC results are available and shown that his/her biochemical is not controlled, the investigator schedules a visit for patient to come to the clinic and pick up study medication at the next combination dose level.

**Table 6-3      Pasireotide and cabergoline dose modification steps for patients currently treated with maximal tolerated doses of pasireotide monotherapy**

Pasireotide: pasi Cabergoline: cabe	Starting dose level	Dose modification level - 1	Dose modification level - 2
Modification # 1	0.3, 0.6 or 0.9mg bid pasi + 0.5mg qd cabe a	0.3, 0.6 or 0.9mg bid pasi + 0.5mg every other day cabe a	Discontinuation if no clinical benefit
Modification # 2	0.3, 0.6 or 0.9mg bid pasi + 0.5mg qd cabe b	0.3, 0.6 or 0.9mg bid pasi + 1.0mg qd cabe a	
Modification # 3	0.3, 0.6 or 0.9mg bid pasi + 1.0mg qd cabe a	0.3, 0.6 or 0.9 mg bid pasi + 1.0mg every other day cabe a	0.3, 0.6 or 0.9mg bid pasi + 0.5mg qd cabe

a Dose modification is initiated if the current dose is not tolerated

b Dose modification is initiated if biochemical control is not achieved

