**Figure 6-3 LFT Management Algorithm**

## 6.6 Treatment interruption and treatment discontinuation

Patients experiencing unacceptable toxicity (AE grade 3 or higher) that the investigator considers directly attributable to pasireotide should have their dose reduced or should be withdrawn from the study. [Table 6-4](#) should be regarded as a guideline for the treatment of patients experiencing Adverse Events which are judged to be drug related. Any deviation from these guidelines should be discussed and approved by the sponsor.

If patients permanently discontinued from study treatment without completing the full 35 weeks of treatment in the core phase, the patients will be considered as prematurely discontinued from the study.

All patients must have a safety evaluation 28 days after the last dose of study treatment. Patients who do not complete study completions visit will be documented as a protocol deviation. This applies also to patients who discontinue the trial due to withdrawal of consent unless they do not consent to such a visit. Patients lost to follow up should be recorded as such on the CRF.

Adverse events are described as mild (Grade 1), moderate (Grade 2), severe (Grade 3) or life-threatening (Grade 4). Guidelines for treatment of patients experiencing adverse events are indicated below ([Table 6-4](#)).

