**Table 6-4 Guidelines for treatment of patients experiencing adverse events**

Patients	Adverse Event	Action
All	AE grade $\leq$ 2 (mild to moderate)	No drug adjustments
	AE grade $\geq$ 3 (severe to life-threatening) and judged as pasireotide-related	Reduce dose of by 0.3mg bid. If AE improves to grade $\leq$ 2 within 1 week, increase dose by 0.3mg bid. If AE recurs at grade $\geq$ 3, reduce dose by 0.3mg bid again and remain at lower dose. If AE does not improve to grade $\leq$ 2 within 1 week on lower dose, reduce dose by 0.3mg bid again if possible. If AE does not improve to grade $\leq$ 2 within 1 week on 0.3mg bid patient should be discontinued from study treatment
	AE grade $\geq$ 3 (severe to life-threatening) and judged as cabergoline-related	Reduce dose from daily schedule to every other day schedule. If AE improves to grade $\leq$ 2 within 1 week, increase dose to daily schedule. If AE recurs at grade $\geq$ 3, reduce dose every other day schedule again and remain at that schedule. If AE does not improve to grade $\leq$ 2 within 1 week on the every other day schedule, patient should be discontinued from study treatment
	All patients	For patients experiencing hyperglycemia, the dose should be reduced if severity grade 3 or greater persists despite appropriate management. If the hyperglycemia is considered to be life-threatening, the patient should be withdrawn from study treatment regardless of anti-diabetes treatment
	AE grade 3 – All patients	NCI-CTCAE v4.03 grades diabetes that is treated with insulin as a grade 3. However, diabetes grade 3 will require a study drug dose reduction only in cases of uncontrolled hyperglycemia despite appropriate management. Patients who despite appropriate therapeutic interventions and dose reduction of study drug, develop uncontrolled diabetes and/or consistently high blood glucose values: FPG $\geq$ 240mg/fdL (13.3 mmol/L) or HbA1c value $\geq$ 10% will require study treatment discontinuation
	Hypocortisolism	If a patient shows high sensitivity to pasireotide 0.6 mg bid resulting in cortisol values $<$ LLN and/or signs/symptoms consistent with the diagnosis of hypocortisolism, the dose of pasireotide can be decreased to 0.3 mg bid. Despite the dose reduction, some patients may still present with cortisol values $<$ LLN and/or signs/symptoms consistent with hypocortisolism; in this case the dose of pasireotide can be further reduced to 0.3 mg qd in order to achieve and maintain normal cortisol levels.

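### For patients who enter on pasireotide and do not tolerate cabergoline 1.0 mg every other day, Section 6.4.1 and Table 6-3 give different actions, and Table 6-4 conflicts with the Table 6-3 step for persistent severe events

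*Protocol*

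**What the plan says.** Three places in the protocol bear on a patient who entered on pasireotide, was raised to cabergoline 1.0 mg daily, was reduced to 1.0 mg every other day, and does not tolerate that either.

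- **Section 6.4.1, text for patients already on pasireotide.** "If 1.0mg every other day is not tolerated, and biochemical control is not achieved, patient should be considered for discontinuation". The sentence goes on to require absence of clinical benefit ("patient should be considered for discontinuation if no clinical benefit is derived") and refers the reader to Table 6-3.
- **Table 6-3, Modification #3.** The level -1 cell is "0.3, 0.6 or 0.9 mg bid pasi + 1.0mg every other day cabe". It carries footnote a: "Dose modification is initiated if the current dose is not tolerated". The next cell, level -2, is "0.3, 0.6 or 0.9mg bid pasi + 0.5mg qd cabe". The row ends there, with no entry for discontinuation.
- **Table 6-4, row for cabergoline-related events of grade 3 or higher.** After reduction to every-other-day dosing, if the event does not come down to grade 2 or lower "within 1 week on the every other day schedule, patient should be discontinued from study treatment". No condition on biochemical control or benefit is attached. Section 6.6 says of this table that it "should be regarded as a guideline for the treatment of patients experiencing Adverse Events which are judged to be drug related", and asks for sponsor approval of departures from it.

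Protocol Section 10.2.3 treats discontinuation before week 31, or between weeks 31 and 35, as non-response for the primary endpoint.

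**The concern.** The text cites a table for an action that the relevant row of the table does not show. An investigator who follows the text considers stopping an uncontrolled patient without benefit; one who follows the row moves the same patient to another cabergoline schedule and continues. Where the intolerance is a persistent severe cabergoline-related event, Table 6-4 adds an unconditional stop, which cannot be carried out together with the Table 6-3 step.

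Two things are at stake. The first is the handling of severe toxicity, where a single instruction is most needed. The second is the primary endpoint: a patient who stops is a non-responder by rule, while a patient who stays on treatment can still be counted as a responder at week 35.

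**Working it through.** **1. Is this a shorthand used throughout the tables?** No. Each row that deals with intolerance of an every-other-day schedule can be compared with its own text:

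- Table 6-2 #6 (untreated patients, 0.5 mg every other day): ends in discontinuation if there is no benefit. Agrees with the text.
- Table 6-2 #7 (untreated patients, 1.0 mg every other day): the same. Agrees with the text.
- Table 6-3 #1 (pasireotide-treated patients, 0.5 mg every other day): the same. Agrees with the text.
- Table 6-3 #3 (pasireotide-treated patients, 1.0 mg every other day): leads to 0.5 mg daily. Does not agree with the text.

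Only the last departs from the sentence that cites it.

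**2. What the Table 6-3 step does to the dose.** Average dose = amount per intake / days between intakes.

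- 1.0 mg every other day: 1.0 / 2 = 0.5 mg per day; × 7 = 3.5 mg per week.
- 0.5 mg daily: 0.5 / 1 = 0.5 mg per day; × 7 = 3.5 mg per week.
- Over 14 days: 7 × 1.0 = 7.0 mg and 14 × 0.5 = 7.0 mg.

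The average is unchanged. The amount per intake halves and the number of intakes doubles. The step also returns the patient to daily dosing, whereas Table 6-4 uses the move from daily to every-other-day dosing as its reduction.

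**3. Which instructions meet in which patient.**

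- *Intolerance below grade 3, uncontrolled, no benefit:* the text says consider stopping; Table 6-3 says 0.5 mg daily. Two-way conflict.
- *Intolerance below grade 3, controlled or benefiting:* the text gives no action; Table 6-3 says 0.5 mg daily. A gap in the text, not a contradiction.
- *Cabergoline-related event of grade 3 or higher, not improved after a week on the every-other-day schedule:* Table 6-4 says stop; Table 6-3 says 0.5 mg daily; the text says consider stopping only if there is neither control nor benefit. Table 6-3 conflicts with Table 6-4 in every such patient, and with the text in those without control or benefit.

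**4. Size for the primary proportion.** Inputs: N = 64 and a planned maximum of 6 patients entering on pasireotide (Protocol Section 10.5).

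- One patient whose status changes: 1/64 = 1.6 points.
- Two patients: 2/64 = 3.1 points.
- Arithmetic ceiling, all six: 6/64 = 9.4 points.

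The Amendment 2 summary records 2 such patients among the first 52 enrolled. For scale, Section 10.5 states a precision of 12.8 points for the 95% confidence interval.

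**The case against.** The strongest reply is that most of this is two rules with different triggers. Table 6-4 is a guideline for severe drug-related events, while Section 6.4.1 and Table 6-3 speak of intolerance without a grade. A reader might infer three different actions for one trigger. The documents do not support that: all three meet only for a persistent cabergoline-related event of grade 3 or higher, and two of the three actions are discontinuation, one conditional and one not. This part of the reply stands and limits the point. It does not remove the mismatch between the text and the table it cites.

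Second, Table 6-3 can be read as a sequence: #3 ends at 0.5 mg daily, which is the starting cell of #1, and #1 ends in discontinuation if there is no benefit. That is a possible reading, but the same cell also starts #2, which leads back to 1.0 mg daily, and the text attaches discontinuation directly to failure of 1.0 mg every other day. The sequence does not reproduce the text.

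Third, a reader might infer from the equal weekly average that the Table 6-3 step is no reduction and therefore pointless. The documents do not support this. The amount per intake is halved, and nothing in the protocol says whether tolerability follows the weekly average or the single intake. That is a clinical question and is left open here.

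Fourth, the text's action reaches only uncontrolled patients without benefit. Many of them would be non-responders anyway, and Section 7.1.2.1 already requires withdrawal for persistently raised UFC without clinical benefit after three months or more. This stands. Responder status changes mainly for a controlled patient stopped under Table 6-4, or for one who would have reached control by week 35 if kept on treatment.

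**Conclusion.** The contradiction is real and minor. For patients who enter on pasireotide, Section 6.4.1 cites Table 6-3 for an action that Modification #3 does not show, and for persistent severe cabergoline-related events the Table 6-3 step cannot be squared with Table 6-4. Untreated patients are outside the Table 6-3 conflict: Table 6-2 #7 agrees with its text, and only a difference in force from Table 6-4 remains.

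Each reclassified patient moves the primary proportion by 1.6 points. The 9.4-point figure might be taken as the likely effect, but it is not an expected value. It requires all six planned patients to be raised to 1.0 mg, to fail both 1.0 mg schedules, and to change status as a result. The planned maximum of 6 is itself an assumption of the sample-size section. The trial is exploratory with no formal test, so no decision threshold is affected.

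The link to non-response rests on Protocol Section 10.2.3. A reader might infer that the SAP confirms it. SAP Section 6.5.1 states last observation carried forward for the core phase and refers to a Section 8.3.2 that is not in the text available for review, so the SAP neither confirms nor refutes it here.

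**What to change.** Reconcile Section 6.4.1, Table 6-3 Modification #3 and Table 6-4 so that one action follows for each trigger: intolerance below grade 3, and a cabergoline-related event of grade 3 or higher that persists on the every-other-day schedule. State which rule takes precedence where both triggers are met, and what applies to an intolerant patient who is controlled or benefiting. Which action is right is for the sponsor's medical team.

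The cost is wording in one section and two tables; sample size, endpoint and analysis do not change. Because the SAP's final cut-off (30 June 2019) has passed, the practical minimum is a short listing in the study report. It should show any patient who entered on pasireotide and did not tolerate 1.0 mg every other day, the instruction followed, the resulting week-35 responder status, and the missing-data rule used to assign that status. If there are none, one sentence saying so closes the point.
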